11.3 Telephone based interviews

- From the main sample (n=42) we will purposively subsample between 12-16 participants as is standard practice for the generation of qualitative data using an interpretative phenomenological approach (IPA) [61]. Semi-structured, telephone-based interviews will be conducted to minimise the potential burden on participants by avoiding the need for attending further research appointments [62].
- All consenting intervention clinicians (up to approximately n=12 across all 3 sites) will be invited to participate in semi-structured telephone-based interviews.

12. Study outcome measures

12.1 Feasibility study 1

Measurement properties of primary outcome measures: At present there are no recognised outcome measures for the measurement of lower limb function that have been used for the early RA population. Promising instruments exist but these have not been used specifically in the early RA population and therefore important information concerning measurement properties such as 'meaningful levels of change' and 'responsiveness' are lacking. To address this gap, responsiveness and meaningful levels of change of primary outcome measure candidates will be evaluated at 12 weeks from randomisation using anchor and distribution-based approaches [63-65].

The foot function index disability subscale (FFIdis) is a 9-item, foot-specific patient-reported outcome measure designed to measure self-reported foot-related disability and which was developed using classical test theory for people with RA. Item response is via 100mm visual analogue scales to indicate level of difficulty experienced in the previous week due to foot problems. The item scores are summed, divided by the maximum possible sum of the item scores and then multiplied by 100. The scores range from 0 to 100; higher the scores reflect more severe foot-related disability respectively. It has a high degree of internal consistency, good test –retest reliability, is considered to be responsive to change [66-70] and has been widely used in observational studies and trials of foot interventions in established RA [71,72]. Moreover, the FFIdis is quick and simple to use and has excellent face validity with the inclusion of items relevant to functional walking tasks such as "Walking outside", "Climbing stairs", and "Standing up from a chair".

The Patient Reported Outcome Measurement Information System physical function short form (PROMIS PF- 20) is a 20-item, generic patient-reported outcome measure designed to measure self-reported physical functional ability and which is based on item response theory (IRT) [73]. Item response is via 5-point likert scale to indicate current level of difficulty in undertaking tasks related to physical function, and scoring is conducted by summing raw item scores, multiplying them by the number of items in the short form, and dividing by the by the number of items that were answered. Raw scores are then translated to a T-score for each participant [74]. PROMIS PF-20 has emerged as a valid and reliable outcome measure of physical function in rheumatoid arthritis which is now considered to have greater responsiveness and precision relative to traditional legacy instruments such as the health assessment questionnaire (HAQ) and short form 36 (SF36) [75,76]. Moreover, short forms can be customised from a PROMIS PF item bank in order to more optimally reflect those aspects of physical function that are relevant for early RA patients with foot problems [75].

Walking velocity is an objective measure of walking capacity/functional mobility that has been used as an outcome measure in several studies in RA [7]. It appears to be one of the strongest independent predictors of higher disability scores in RA populations who have foot involvement [77]. Typically, time taken to walk a specified distance, or distance walked within a specified time are used to evaluate self-selected walking velocity [77]. For the purposes of this study we will seek to measure 10-metre walking velocity using a marked unobstructed distance of 10-metres and a stopwatch. Measurement of walking velocity is considered to be valid and reliable, and previous research suggests that it may be sensitive to change in the RA population [25,78-79].

The recent-onset arthritis disability questionnaire lower extremity subscale (ROADles) is a 4item early RA specific questionnaire designed to measure lower extremity physical function [80-83]. In relation to the previous week, subjects are asked to rate the level of difficulty in performing lower extremity function tasks on a 5 point likert scale (0 without any difficulty, 4 unable to do). Scoring is by summating the 4 items (score 0-16) then normalisation to a 0-10 scale by multiplying the raw scores by 0.625. The ROADles is considered to be valid, reliable and responsive to change [80-83].

12.2 Feasibility study 2

Evaluation of intervention acceptability, adherence and safety: We will undertake a complementary mixed-methods evaluation of intervention acceptability, adherence and safety. These feasibility outcomes will be collected following completion of the 12-week intervention period.

Intervention acceptability will be evaluated using a 3-item questionnaire which utilises 5-point Likert scales for responses. This questionnaire has been adapted from previous literature and has been used by one of our co-applicants (NF) with success in previous trials [84,85]. Questions and responses include: "How confident are you that the treatment can help the Version Date: 11th Feb 2018 Version Number: 1.2

problem?" (not at all to very), "Would you recommend the treatment to a friend with a similar problem?" (not at all confident to very confident), "Does the treatment make sense to you?" (not at all logical to very logical). For analysis, responses will be dichotomised to positive (higher 2 responses) and negative (lower 3 responses) in order to evaluate percentages of participant acceptability for progression criteria.

Treatment adherence will be examined using the Exercise Adherence Rating Scale (EARS) which is a valid and reliable self-reported measure of adherence to exercise therapies developed by one of our co-applicants (EG) [86]. The EARS has 6-items generated from a systematic review and interviews with patients, physiotherapists and psychologists. Items are scored using a 5-point Likert scale (completely agree to completely disagree), resulting in a possible score between 0-24, where a higher score indicates greater adherence [86].

To monitor safety arising as a result of the intervention, serious adverse events (SAEs), and expected events will be recorded. The physiotherapists or podiatrists delivering the intervention will record SAEs during each intervention session, using a SAE reporting form according to the Glasgow CTU standard operating procedures for RCTs. Participants and the local personnel (intervention clinicians and outcome assessors) may report SAEs to the study team at any time. In addition, at the end of the intervention period the independent outcomes assessor will ask participants whether or not they have experienced SAEs over the 12-weeks intervention period. Expected events (defined as specific non-serious events that might be related to the intervention) will be monitored and recorded using a standard form as part of the case report form (CRF). These will be evaluated by the trial management group (TMG) to determine these are related to the intervention or study and will therefore be recorded as adverse events. Adverse events will then be reported to the trial steering committee (TSC). Given the study population, expected harms might include falling, fatigue, pain and post-exercise muscle soreness (see section 5. Assessment of Safety).

As part of this mixed methods evaluation, we will also undertake qualitative research according to the interpretive phenomenology approach (IPA) in order to elaborate, enhance and clarify the results from the quantitative component outlined above (complementary mixed methods approach) [87]. From the main sample (n=42) we will purposively subsample between 12-16 participants as is standard practice for the generation of qualitative data using an IPA [88]. Semi-structured, telephone-based interviews will be conducted to minimise the potential burden on participants by avoiding the need for attending further research appointments [62]. The interviews will be arranged on a date and at a time that is convenient to participants. The data collection will commence with an opening question which will allow the participant to talk freely about their experiences. This conversational style of one to one interview allows for the data to be generated more by the participant form their own perceptions and personal experiences. Further, it allows then to reveal their true feelings and opinions without the pressure or influence of a peer group. The opening question will be followed by several trigger questions in order to keep the conversation focussed. The interview will be recorded using an adapted digital recorder.

Version Date: 11th Feb 2018

12.3 Feasibility study 3

- Evaluation of intervention fidelity: Fidelity of intervention delivery and uptake will be evaluated using a complementary mixed-methods design. Data will be gathered from participants and trial intervention clinicians from various sources as listed below
- An intervention checklist will be completed by all intervention therapists after each intervention session. The checklist will permit assessment of intervention protocol deviations.
- Semi-structured telephone-based interviews with all consenting intervention clinicians. Interviews will explore clinicians' experiences and perceptions of delivering the intervention.
- Audio-recordings of all clinician-participant consultations will be undertaken. A random sample of 10% of gait rehabilitation consultations from each site will be evaluated objectively by independent observers using an intervention fidelity checklist and the Motivational Interviewing Treatment Integrity Scale (MITI). The MITI is a valid and reliable measure designed to evaluate the clinicians' MI skills [88].
- Participants' usual care will be recorded at the end of the 12 week intervention period using a modified version of the client service receipt inventory (CSRI). The CSRI provides a standardised method of collecting information on healthcare use including medications, admissions, referrals, consultations with and care provided by other healthcare professionals, and self-care [89].

13. Assessment and reporting of safety and serious adverse events

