13.2 Definitions of Adverse Events

Adverse Event (AE) - Any untoward medical occurrence in a subject to whom the intervention has been administered, including occurrences which are not necessarily caused by or related to the intervention.

Serious Adverse Event (SAE) - Any adverse event or adverse reaction that a) results in death b) is life threatening Version Date: 11th Feb 2018 c) requires hospitalisation or prolongation of existing hospitalisation

- d) results in persistent or significant disability or incapacity
- e) consists of a congenital anomaly or birth defect.

f) is otherwise considered medically significant by the investigator.

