13.3 Recording and Reporting AEs/SAEs

Participants will be asked at clinical visits whether or not they have experienced any adverse effects from the study intervention or study procedures. All AEs will be recorded in participant's clinical notes.

- AEs and SAEs occurring before enrollment will not be recorded or reported.
- Participants will be asked at each study visit about the occurrence of any AEs.
- All SAEs occurring within the 12 weeks of the intervention will be recorded.
- All AEs must be assessed for seriousness. SAEs must be assessed for causality, expectedness and severity.
- An SAE occurring to a research participant must be reported to the main Research Ethics Committee (REC) within 15 days of notification, where in the opinion of the Chief Investigator the event was:

"Related" that is, it resulted from administration of any of the research procedures And

"Unexpected" that is the type of event is not an expected occurrence as a result of the intervention provided.

Causality - This should be assessed by the CI or PI and should be described using the following categories:

- Unrelated to intervention
- Possibly related to intervention
- Probably related to intervention
- Definitely related to intervention

Severity - This should be assessed by the CI or PI and should be described using the following categories:

Mild:	awareness of event but easily tolerated
Moderate:	discomfort enough to cause some interference with usual activity
Severe:	inability to carry out usual activity

Details of SAE's arising during the trial should be entered in to the Non-cTIMP SAE reporting form, provided to the research sites. The site must enter details in the form and submit to the sponsor contact provided within 24 hours of first becoming aware of the event and any follow Version Date: 11th Feb 2018 Version Number: 1.2

up information should also be reported. Such events must be reported to sponsor in order to capture all potential related adverse events.

SAE forms should be completed and sent with 24 hours of becoming aware to a member of the GREAT study team at Glasgow Caledonian University, using the designated SAE form for non-CTIMPs using the designated email inbox.

The paper SAE form should be completed and emailed to: [contact]

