Selection of primary outcome for the future randomised trial: For the second iteration, results of the analyses of the primary outcome candidates from the feasibility phase will be compiled in a report which will be presented to the both the TMG and the TSC who will be tasked with recommending which outcome should be taken forward to the main RCT. The TMG will be asked to consider the relative simplicity of the candidate outcome measures (to reduce participant burden), the strength of correlations with the anchor, and responsiveness.

16. Analysis of process outcomes

Remaining analyses will focus on process measures. Analyses will include the following aspects:-

- Acceptability of the intervention will be evaluated using: 3-item acceptability questionnaire and analysed using descriptive statistics and thematic analysis of qualitative data (from participants and clinicians).
- Treatment adherence will be evaluated using: the Exercise Adherence Rating Scale (EARS) and will be summarised using descriptive statistics and thematic analysis of qualitative data (obtained from participants and clinicians).
- Safety of the intervention will be determined by analysis of all reported adverse events and thematic analysis of qualitative data from participants and clinicians.
- Intervention fidelity data will be gathered from participants and trial intervention clinicians and analysed as follows:-

i) deviations from intervention protocols will be recorded using intervention checklists and will be analysed using descriptive statistics.

ii) thematic analysis of qualitative data obtained from clinicians.

iii) audio samples of clinician-participant consultations will be evaluated objectively by independent assessors using an intervention fidelity checklist and the motivational interviewing treatment integrity scale.

For deeper explorations of intervention acceptability, adherence and safety the interview data will be transcribed verbatim. Thematic analysis will be undertaken using a thematic network approach whereby basic themes (lowest order premises) will be grouped together to summarise more abstract principles (organising themes) and global themes which wholly encapsulate the phenomena [109].

17. Software for statistical analysis

Statistical analyses will be carried out using standard statistical software, such as SAS or R.

18. Sample size

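### Section 12.2 contradicts sections 13.2 to 13.4 on what counts as an adverse event, and non-serious events off the expected list have no stated route into the study data

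*Protocol*

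**What the plan says.** Section 12.2 (Feasibility study 2) sets the recording rule for the safety outcome: "serious adverse events (SAEs), and expected events will be recorded". It then says: "Expected events (defined as specific non-serious events that might be related to the intervention) will be monitored and recorded using a standard form", that form being part of the CRF. The TMG evaluates these events to "determine these are related to the intervention or study and will therefore be recorded as adverse events", and adverse events then go to the TSC. At the end of the intervention the independent outcomes assessor "will ask participants whether or not they have experienced SAEs over the 12-weeks intervention period".

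Section 13 is wider:

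- 13.2 defines an AE as any untoward medical occurrence, "including occurrences which are not necessarily caused by or related to the intervention".
- 13.3 states: "Participants will be asked at each study visit about the occurrence of any AEs". It requires a seriousness assessment for all AEs and a causality assessment for SAEs. The one place it names for recording AEs in general is the clinical notes.
- 13.4 puts all expected AEs on the CRF with onset date, seriousness, severity, need for medication and outcome. The data centre then produces SAE and AE reports for the TSC. It states no relatedness condition.

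The schedule of assessments (section 4) ticks an adverse event review at Visit 2 but leaves its description blank. Section 16 states: "Safety of the intervention will be determined by analysis of all reported adverse events", together with thematic analysis of the interviews.

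**The concern.** Objective 3 (section 6) covers adverse and unintended outcomes, and section 13.1 says the intervention has not been used in early RA. The events that nobody thought to list are therefore the ones that would add most. They are also the class for which the protocol names no study form.

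The relatedness condition in 12.2 raises a second problem. In a single-arm study there is no comparison group against which to judge relatedness, so it rests on the opinion of the group running the study. It is useful as a recorded attribute of an event. As a condition for being an AE at all, it conflicts with the protocol's own definition and leaves the contents of the safety analysis unclear. An analysis plan could choose how to tabulate the events that were collected, but it could not recover events that never reached the database.

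**Working it through.** No arithmetic applies, because the protocol states no event rate or safety figure to reproduce. The check is to follow each class of event through the sections.

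| Class of event | AE under 13.2? | AE under 12.2? | Stated place of recording |
|---|---|---|---|
| SAE not on the 13.4 list | Yes | Yes | SAE form (12.2, 13.3) |
| Expected event, judged related | Yes | Yes, after TMG review | CRF (12.2, 13.4) |
| Expected event, judged unrelated | Yes | Not on the natural reading | CRF (12.2, 13.4) |
| Non-serious event not on the list | Yes | Not among the classes recorded | Clinical notes (13.3) |

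**Direction.** Every event that is an AE under 12.2 is also one under 13.2, but rows three and four are AEs under 13.2 only. The 12.2 set is thus a subset, and its count can only be equal or lower.

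**Row three.** The data are kept, since the CRF entry comes before the TMG review in 12.2 and is unconditional in 13.4. What depends on the section followed is the AE label, and so possibly the event's place in TSC reports and the section 16 analysis. The CRF fields listed in 13.4 include no relatedness item, and 13.3 asks for causality only for SAEs. The judgement that 12.2 relies on therefore has no stated field.

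**Row four.** The CRF details in 13.4 are for expected AEs, and the form in 13.3 is for SAEs. Neither covers this class. Section 21 makes the CRF the vehicle for study data sent to the data centre and mentions no transfer from clinical notes. The Visit 2 review in section 4 names no form, and the Visit 2 procedures in section 11.2 omit it.

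**The 12-week question.** It covers SAEs in 12.2 and any AE in 13.3.

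**Two further mismatches in the same text.** First, 12.2 defines expected events as non-serious, while 13.4 provides for SAEs that meet the expected list. Second, 12.2 names falling as an expected harm without limit, while 13.4 lists trips, slips and falls only around the circuit. Whether a non-serious fall elsewhere is recorded as expected depends on the section read.

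**Interviews as a back-up.** They cover 12 to 16 of 42 participants, so 42 - 16 = 26 to 42 - 12 = 30 would not be interviewed.

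**The case against.** The strongest case against is that section 13 already contains the right rule. Section 13.3 asks about any AE at each study visit, section 4 schedules an adverse event review at Visit 2, and 12.2 introduces its SAE question as an addition to other routes. Section 13.4 records all expected AEs without a gate. Recording SAEs plus a prespecified list can also be a reasonable choice for a non-drug study described as very low risk. The CRF and the data management plan are not at hand and may contain a general AE page. All of this stands, and it limits the point to a contradiction and a gap in routing.

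A reader might go further and infer that the protocol under-counts harm by rule, or that unlisted non-serious events never reach the CRF, the TSC or the analysis. The document does not support that. Section 13.3 sends AEs to the clinical notes without saying that they go nowhere else. The 12.2 sentence on relatedness is poorly constructed: a gate is its natural reading, but it does not say that related events alone count. Expected events judged unrelated remain on the CRF in any case.

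A reader might also apply an assumed event rate to the 42 participants to size the loss. The protocol offers no basis for such a rate.

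The objection does not remove the conflict. Site staff following 12.2 and site staff following 13.2 to 13.4 would produce different AE sets, and a wider question in 13.3 helps the analysis only if the answer has somewhere to go.

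**Conclusion.** The point holds as an internal contradiction with a gap in data routing. Section 12.2 applies a narrower meaning of adverse event than 13.2 to 13.4, and no route into the study database is stated for non-serious events off the expected list. As a result, the set of events behind the section 16 safety conclusion is not fixed and may omit them.

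The direction is certain: following 12.2 gives an AE set equal to or smaller than the one 13.2 defines. The size is unknown and cannot be computed from the document. The conclusion assumes that the 12.2 sentence is read as a condition and that neither the CRF nor the data management plan supplies the missing route. It should be corrected, because the safety objective depends on it and the correction is small.

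**What to change.** 1. Apply the 13.2 definition throughout, including in 12.2.
2. In 12.2, remove relatedness as a condition for being recorded as an AE. Record it as a separate CRF field.
3. Align the 12-week question in 12.2 with 13.3, so that it covers any AE.
4. Add a free-text AE line to the CRF, so that unlisted non-serious events elicited under 13.3 reach the data centre and the TSC. Name this form against the adverse event review in section 4 and add the review to section 11.2.
5. Report all AEs to the TSC and in the section 16 analysis, with related AEs as a subset.
6. Reconcile 12.2 and 13.4 on whether an expected event can be serious, and on which falls count as expected.

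The cost is a protocol amendment limited to wording, one extra CRF line with a relatedness field, and slightly more data entry.
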